## **4. PARTICIPANT ENTRY**

### **4.1 PRE-REGISTRATION EVALUATIONS**

Women opting to undergo outpatient hysteroscopy

### **4.2 INCLUSION CRITERIA**

1. Age 18-70
2. Patients undergoing outpatient hysteroscopy for any indication
3. Capacity to give informed consent
4. Cognitive and linguistic ability sufficient to understand and fill out the NRS questionnaire.

### **4.3 EXCLUSION CRITERIA**

1. Epilepsy
2. Severe vertigo
3. Significant hearing impairment
4. Blindness
5. Current facial injury /burn
6. Patients who have not given informed consent
7. Patients aged less than 18 or more than 70.

### **4.4 WITHDRAWAL CRITERIA**

Participant request

## **5. ADVERSE EVENTS**

## 5.1 DEFINITIONS

**Adverse Event (AE):** any untoward medical occurrence in a patient or clinical study subject.

**Serious Adverse Event (SAE):** any untoward and unexpected medical occurrence or effect that:

- **Results in death**
- **Is life-threatening** – *refers to an event in which the subject was at risk of death at the time of the event; it does not refer to an event which hypothetically might have caused death if it were more severe*
- **Requires hospitalisation, or prolongation of existing inpatients' hospitalisation**
- **Results in persistent or significant disability or incapacity**
- **Is a congenital anomaly or birth defect**

Medical judgement should be exercised in deciding whether an AE is serious in other situations. Important AEs that are not immediately life-threatening or do not result in death or hospitalisation but may jeopardise the subject or may require intervention to prevent one of the other outcomes listed in the definition above, should also be considered serious.

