## 5.3 REPORTING PROCEDURES

All adverse events should be reported. Depending on the nature of the event the reporting procedures below should be followed. Any questions concerning adverse event reporting should be directed to the Chief Investigator in the first instance.

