### 5.3.1 Non serious AEs

All such events, whether expected or not, should be recorded.

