### 5.3.2 Serious AEs

An SAE form should be completed and faxed to the Chief Investigator within 24 hours.

All SAEs should be reported to the Greater Manchester East Research Ethics Committee where in the opinion of the Chief Investigator, the event was:

- 'related', i.e. resulted from the administration of any of the research procedures; and
- 'unexpected', i.e. an event that is not listed in the protocol as an expected occurrence

Reports of related and unexpected SAEs should be submitted within 15 days of the Chief Investigator becoming aware of the event, using the NRES SAE form for non-IMP studies. The Chief Investigator must also notify the Sponsor of all related and unexpected SAEs.

Local investigators should report any SAEs as required by their Local Research Ethics Committee, Sponsor and/or Research & Development Office.

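### The SAE definition in Section 5.1 includes unexpectedness, which Section 5.3.2 treats as a separate later test, so a serious but expected event can be read as falling outside the 24-hour report

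*Combined protocol and SAP*

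**What the plan says.** Section 5.1 of the protocol gives two definitions. An adverse event is "any untoward medical occurrence in a patient or clinical study subject", with no condition on expectedness. An SAE is "any untoward and unexpected medical occurrence or effect that" meets at least one seriousness criterion: death, threat to life, hospitalisation or its prolongation, lasting disability, or congenital anomaly. A closing paragraph allows medical judgement about seriousness in other situations, and it refers to "Important AEs that are not immediately life-threatening or do not result in death or hospitalisation".

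The reporting rules follow in Section 5.3:

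- The general rule is "All adverse events should be reported". No time limit is given, and the reader is sent to the procedures beneath it.
- Section 5.3.1, for non-serious events, says "All such events, whether expected or not, should be recorded".
- Section 5.3.2, for SAEs, says "An SAE form should be completed and faxed to the Chief Investigator within 24 hours". It then limits ethics committee reporting to SAEs that the Chief Investigator considers both related and unexpected, and explains the second term as "an event that is not listed in the protocol as an expected occurrence". The timing is "Reports of related and unexpected SAEs should be submitted within 15 days of the Chief Investigator becoming aware of the event".

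The protocol text contains no list of expected occurrences.

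**The concern.** Seriousness and expectedness are different judgements. Seriousness concerns the outcome of the event. Expectedness concerns whether it was foreseen. Section 5.3.2 keeps them apart: all SAEs go quickly to the Chief Investigator, and a subset goes on to the committee. Section 5.1 merges them by making unexpectedness a condition of being an SAE at all.

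The person deciding whether to complete an SAE form applies Section 5.1 first. That section neither defines *unexpected* nor points to a definition elsewhere. Someone who takes the word in its ordinary sense could conclude that an admission for a recognised complication of hysteroscopy is not an SAE, and so complete no form. At stake is whether the Chief Investigator hears of such an event within 24 hours, and whether it is classified as serious.

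**Working it through.** The plan gives no figure on this point and no arithmetic applies. The check sets the definition against the reporting rules.

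**Step 1: do Sections 5.1 and 5.3.2 fit together?** By Section 5.1, every SAE is unexpected. Section 5.3.2 then selects the unexpected ones from among the SAEs. If the word means the same in both places, the second test excludes nothing. A test that can exclude nothing suggests that expectedness was meant to be judged after an event had been classed as an SAE. The adverse event definition, which has no such condition, points the same way.

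**Step 2: where does each kind of event go?** Two readings of *unexpected* in Section 5.1 are possible: the ordinary meaning, or the list test of Section 5.3.2 carried back.

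| Event | Ordinary meaning in 5.1 | List test carried back to 5.1 |
|---|---|---|
| Serious, not foreseen | SAE, 24-hour form | SAE, 24-hour form |
| Serious, foreseen (for example, admission for a known complication) | Not an SAE by the listed criteria, and not non-serious; only the untimed rule of 5.3 applies | SAE, 24-hour form (no list exists, so nothing counts as expected) |
| Non-serious, foreseen or not | Recorded under 5.3.1 | Recorded under 5.3.1 |

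The readings differ only in the second row. On the ordinary meaning, the protocol explicitly covers minor expected events but has no specific procedure for serious expected ones.

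**Step 3: does the medical-judgement paragraph fill the gap?** Not clearly. Its more specific sentence concerns events short of death, immediate threat to life or hospitalisation. The foreseen event in the table does lead to hospitalisation.

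**Step 4: what remains for such an event?** Section 5.3 still requires it to be reported, without a deadline. Section 3 lists complications among the items recorded for each patient, and Section 3.1 makes complication rate a secondary outcome. Neither depends on the SAE definition. What falls away is the SAE classification and the 24-hour form.

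**The case against.** The strongest reply is that the protocol does explain *unexpected*, in Section 5.3.2, and lists no expected events. Carried back to Section 5.1, that explanation makes every serious event an SAE and closes the gap. Both passages belong to one short section, and Section 5.3 refers questions to the Chief Investigator. This stands as a limit: the exclusion is one reading, not a certainty. It does not remove the inconsistency. Section 5.1 has no cross-reference to the list test, which is written for committee reporting, and under that test the word excludes nothing in either place, so it serves no purpose in the definition.

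A second reply is that the first sentence of the medical-judgement paragraph speaks of adverse events generally and could be stretched to cover a serious event that misses the definition. That is arguable, but a 24-hour duty should not rest on it.

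Third, the practical reach is modest. If the word has the same meaning in both sections, the set of events sent to the committee does not change. The last planned assessment is the questionnaire before leaving the clinic (Sections 3 and 6), so later admissions may go undetected however Section 5.1 is worded. Both points stand.

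A reader might also infer three stronger claims, which the documents do not support:

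- *Serious expected events would be lost from the trial.* Section 5.3 requires all adverse events to be reported, and Section 3 records complications.
- *Known complications are the most likely serious events here, so most would be affected.* The documents give neither a list nor a rate of serious complications.
- *Because the trial is unblinded, reporters would classify expectedness differently by arm.* Nothing in the documents shows this. SAE count is not a listed outcome, and complication rate and side effects do not depend on the SAE definition.

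**Conclusion.** The point holds as an inconsistency between Sections 5.1 and 5.3.2, with a possible consequence for safety reporting. It rests on the wording alone. The consequence further assumes that a reporter takes *unexpected* in its ordinary sense when applying Section 5.1. If the list test is used instead, no event is excluded and only the redundancy remains.

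The consequence is limited to SAE classification and the 24-hour report to the Chief Investigator. The planned trial has at least 80 patients, and with no event rate in the documents the number of affected events cannot be estimated. Neither the primary comparison of pain and anxiety scores nor the listed safety outcomes are touched. The correction is still worth making, because whether a serious event is reported promptly should not depend on how a reader takes one undefined word.

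**What to change.** Delete the words *and unexpected* from the SAE definition in Section 5.1, so that seriousness alone decides whether an event is an SAE and triggers the 24-hour form. Keep expectedness only in Section 5.3.2, as a criterion for ethics committee reporting. There, either list the expected occurrences to which the text refers or state that none are listed.

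The cost is two words deleted, a sentence or short list added, and possibly a few more SAE forms. Treatment, sample size and analysis do not change.

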## 5.3 REPORTING PROCEDURES

All adverse events should be reported. Depending on the nature of the event the reporting procedures below should be followed. Any questions concerning adverse event reporting should be directed to the Chief Investigator in the first instance.

### 5.3.1 Non serious AEs

All such events, whether expected or not, should be recorded.

### 5.3.2 Serious AEs

An SAE form should be completed and faxed to the Chief Investigator within 24 hours.

All SAEs should be reported to the Greater Manchester East Research Ethics Committee where in the opinion of the Chief Investigator, the event was:

- 'related', i.e. resulted from the administration of any of the research procedures; and
- 'unexpected', i.e. an event that is not listed in the protocol as an expected occurrence

Reports of related and unexpected SAEs should be submitted within 15 days of the Chief Investigator becoming aware of the event, using the NRES SAE form for non-IMP studies. The Chief Investigator must also notify the Sponsor of all related and unexpected SAEs.

Local investigators should report any SAEs as required by their Local Research Ethics Committee, Sponsor and/or Research & Development Office.

**CI email (and contact details below)**

## 6. ASSESSMENT AND FOLLOW-UP

Definition of end of study: when final participant has been recruited within 1 year study period and has had filled out their post procedure NRS questionnaire. Incidental findings are not expected in this study. Any clinically relevant incidental findings that do occur during this study will be reported to the GP for ongoing care as necessary.

## **7. STATISTICS AND DATA ANALYSIS**

Normally distributed data will be analysed using IBM SPSS software. Comparisons will be done with between intervention group and controls with a p value less than 0.05 used to indicate statistical significance.

Means NRS scores will be compared between the 2 groups using the unpaired student's T test.

Data and all appropriate documentation will be stored for a minimum of 5 years after the completion of the study, including the follow-up period.

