**STUDY SUMMARY**

**TITLE** Does Virtual Reality Technology Reduce Pain and Anxiety During Outpatient Hysteroscopy? A Randomised Controlled Trial

**DESIGN** Randomised controlled trial

**AIMS** To evaluate whether the use of virtual reality technology can reduce pain and anxiety during outpatient hysteroscopy procedures.

**OUTCOME MEASURES** Primary outcome measures are patient reported NRS (numeric rating score) for pain and anxiety.  
Secondary outcome measures will be length of procedure, complication rate, reported side effects, procedure completion or if stopped, hysteroscopy findings and type of procedure performed.

**POPULATION** Women aged referred from general gynaecology clinics for outpatient hysteroscopy procedures.

**ELIGIBILITY** Inclusion criteria are age 18-70, capacity to give informed consent and cognitive and linguistic ability sufficient to understand and fill out the NRS questionnaire. Exclusion criteria are epilepsy or severe vertigo, blindness or significant hearing impairment and recent facial injury/burn

**DURATION** 1 year

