## **1.2 RATIONALE FOR CURRENT STUDY**

The purpose of this study would be to determine if the use of VR technology can reduce pain and anxiety experienced by patients during outpatient hysteroscopy procedures when compared to standard pain management.

The optimal method of controlling pain and anxiety during outpatient hysteroscopy is poorly understood and there is a wide variation in clinical practice. This study aims to test whether VR technology could reduce pain and anxiety as a relatively simple and safe adjunct to conventional pain management. Although VR has been used in a variety of clinical settings to date, there is only one previous study investigating the use of VR in an outpatient hysteroscopy setting (Deo et al 2020). This existing trial established that the use of VR is feasible in the OPH setting and that it was effective with significant improvements in patient reported anxiety and pain scores compared to conventional pain management. However, as the authors themselves acknowledge, it involved relatively small numbers (20 patients in control and intervention group respectively). The rationale of this study would be to build upon this evidence by performing the first large scale adequately powered randomised control trial of the use of VR technology in this setting.

We hypothesise that the use of VR technology will significantly improve pain and anxiety when compared to conventional pain management. Finding additional low risk ways of improving pain and anxiety during OPH is of critical importance in order to improve patient experience and the success rate of the procedure as pain is a major reason for unsuccessful OPH procedures.

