## **2. STUDY OBJECTIVES**

The primary objectives of this study are to determine if:

- 1) VR technology can reduce pain during outpatient hysteroscopy?
- 2) VR technology can reduce anxiety during outpatient hysteroscopy?

The secondary objectives of this study are to determine if:

- 1) The use of VR technology feasible during outpatient hysteroscopy?
- 2) The use of VR during outpatient hysteroscopy reduces the procedure failure rate?
- 3) The use of VR increases the outpatient hysteroscopy appointment time?

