### 3. STUDY DESIGN

The study design is an unblinded randomised controlled trial. This study design was chosen as it will provide the best quality of evidence with reduced bias compared to other study designs. A randomised controlled trial is also very feasible in this scenario. Neither the researchers nor the participants will be blinded as to which study arm they are in, as it would be impractical to do so with a VR headset used in the intervention group. The study will be adequately powered with a power calculation based upon findings from previous studies, meaning at least 40 patients will be included in each arm (at least 80 patients in total).

Patients will be randomly allocated by computer allocation to either the intervention or the control group. The intervention group will undergo OPH with standard care plus the use of VR technology administered through a headset with the option of wearing headphones (at the patient's discretion) or having the accompanying sound played aloud. The control group will undergo outpatient hysteroscopy with standard care. Standard care in this unit is in line with the RCGOG guidelines and involves advising patients to take ibuprofen and/or paracetamol one hour prior to their procedure unless there are contraindications. Local anaesthetic intracervical block is used at the discretion of the operator and is usually used if dilatation of the cervix is required.

The primary outcome measure will be the reported NRS (numeric rating score) score which is validated score to assess pain and anxiety levels with values from 0-11. The patient will be asked to fill out the NRS score prior to the hysteroscopy and following the hysteroscopy prior to leaving the clinic.

Secondary outcome measures will be length of procedure, complication rate, reported side effects, procedure completion, hysteroscopy findings and type of procedure performed (for example if purely diagnostic or if any operative procedures are performed).

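### Pain NRS and anxiety NRS are both primary and each is tested at p<0.05, but no rule says what counts as success; if either one may, the two-sided false-positive chance is 7.0% to 9.75% (correlation 0.9 to 0, assumed)

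*Combined protocol and SAP*

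**What the plan says.** The Study Summary uses the plural: "Primary outcome measures are patient reported NRS (numeric rating score) for pain and anxiety". Section 2 lists two numbered primary objectives, whether "VR technology can reduce pain during outpatient hysteroscopy" and whether "VR technology can reduce anxiety during outpatient hysteroscopy". The data list in Section 3 records the pain score and the anxiety score as separate items.

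Sections 3 and 3.1 use the singular: "The primary outcome measure will be the reported NRS (numeric rating score) score". They describe this score as covering both pain and anxiety, and they rank neither. Section 1.2 puts the two together in one hypothesis: "We hypothesise that the use of VR technology will significantly improve pain and anxiety when compared to conventional pain management".

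The analysis in Section 7 is brief. Group comparisons are made "with a p value less than 0.05 used to indicate statistical significance", and "Means NRS scores will be compared between the 2 groups using the unpaired student's T test". Nothing says whether one significant result is enough, whether both are needed, which is tested first, or whether the 5% is shared. Nor does Section 7 say which NRS value is compared, although Sections 3 and 3.1 collect the score both before and after the procedure.

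**The concern.** Section 7 as written allows two unadjusted tests, either of which could be presented as the primary result. The text fits three rules: both must succeed (suggested by Section 1.2), each objective stands alone (suggested by Section 2), or one success is enough (nowhere excluded). These rules differ in error rate and in power. If the rule is left open, it can be settled after the results are known. A trial significant on one outcome of two could then be called positive, with a false-positive chance above the nominal 5%.

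**Working it through.** **Inputs from the documents.** Two primary outcomes (Study Summary, Section 2); p<0.05 and an unpaired t-test (Section 7); "at least 40 patients will be included in each arm" (Section 3).

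**Assumptions.** Tests are two-sided, since Section 7 does not give the sidedness. There is one test per outcome. The correlation ρ between pain and anxiety scores is not given, so a range is shown. The power behind the sample size is not given either, so 70%, 80% and 90% are used.

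**Plan's own figure.** The plan states 0.05 per comparison and no overall error rate, so there is no overall figure to reproduce.

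**Error under each rule, with no effect on either outcome.** Z1 and Z2 are standard normal with correlation ρ.

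- Either outcome, any direction: P(|Z1|>1.96 or |Z2|>1.96). At ρ=0 this is 1 − 0.95² = 0.0975.
- Either outcome, VR benefit only: P(Z1>1.96 or Z2>1.96), with the sign set so that positive favours VR. At ρ=0 this is 1 − 0.975² = 0.0494. A single test gives 0.025.
- Both outcomes: P(|Z1|>1.96 and |Z2|>1.96) = 0.05 + 0.05 − P(either). At ρ=0 this is 0.10 − 0.0975 = 0.0025.

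| ρ | Either, any direction | Either, VR benefit only | Both required |
|---|---|---|---|
| 0 | 9.75% | 4.9% | 0.25% |
| 0.5 | 9.1% | 4.5% | 0.9% |
| 0.7 | 8.3% | 4.2% | 1.7% |
| 0.9 | 7.0% | 3.5% | 3.0% |

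Simulated t-tests with 40 per arm (200,000 trials per setting) gave 9.8%, 9.1% and 7.1% for the either-outcome rule at ρ = 0, 0.5 and 0.9. One-sided tests at 0.05 would give 9.75% at ρ=0 and 6.8% at ρ=0.9.

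The both-required rule cannot exceed 5% even if VR truly affects one outcome, because the test on the other must still pass at 5%. Its price is power. If each test has 80% power, joint power is 0.80² = 64% at ρ=0 and 75% at ρ=0.9.

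**Error under Holm.** With no effect on either outcome, Holm makes a false claim only if the smaller p-value is below 0.025. At ρ=0 that chance is 1 − 0.975² = 4.94%; at ρ=0.9 it is 3.6%.

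**Power under Holm at 40 per arm.** The worst case for one outcome is no effect on the other, when power is close to that of a single t-test at 0.025 (78 degrees of freedom).

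| Unadjusted power at 0.05 (assumed) | Effect that gives it | Power at 0.025 |
|---|---|---|
| 70% | 0.562 SD | 59% |
| 80% | 0.634 SD | 71% |
| 90% | 0.734 SD | 84% |

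The loss is smaller if both effects are real. At ρ=0 with 80% per test, power for each outcome is 0.709 + (0.80 − 0.709) × 0.709 = 0.773, or about 77%.

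**The case against.** The strongest reply is that the plan never says either outcome alone makes the trial positive. Section 2 asks two separate questions, and answering each at its own 5% level is a defensible convention. Section 1.2 joins pain and anxiety, which points towards requiring both. Neither reading inflates the error. This stands: a reader might infer that the trial runs at nearly twice its nominal error, and the documents do not support that. They leave the rule open; they do not adopt the either-outcome rule. Equally, Section 1.2 states a hypothesis and not a decision rule, so it does not close the gap.

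A second reply is that the protocol asks only about reduction, so a false claim of harm would not be reported as success. That is fair. The rate that matches the feared claim is 3.5% to 4.9%, below 5% in absolute terms. It is still 1.4 to 2 times the 2.5% that one two-sided test allows in that direction (3.5/2.5 = 1.4; 4.9/2.5 ≈ 2.0).

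A third reply is that a multiplicity rule alone would not settle the analysis, because the tested NRS value is undefined. That also stands, and the variable has to be named in the same amendment.

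**Conclusion.** The plan has two unranked primary outcomes, a 5% threshold for the NRS comparisons and no success rule. That should be fixed before data are seen. The inflation is conditional: 9.75% (correlation 0) to 7.0% (0.9) for any false-positive primary result, or 4.9% to 3.5% against 2.5% for a false claim of VR benefit, and only if one significant outcome may carry the trial. These figures assume two-sided tests, one test per outcome and no effect on either. Under the both-required or separate-objectives reading there is no inflation, but the plan commits to neither.

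A reader might also infer that the trial must enrol more patients. That does not follow: Holm or a fixed order controls the error at any sample size, and the power behind 40 per arm is not stated.

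**What to change.** Before any data are seen, add to Section 7 a statement such as: *The two primary outcomes are the pain NRS and the anxiety NRS, each defined as [one named variable, for example the post-procedure score]. They are tested with the Holm procedure at an overall two-sided 5% level: the smaller p-value against 0.025 and, if significant, the other against 0.05.*

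Holm suits the present text because neither outcome is ranked. A pre-stated fixed order is an acceptable alternative: the first outcome is tested at 0.05, and the second at 0.05 only if the first is significant. The singular and plural wording in the Study Summary and Sections 3 and 3.1 should then be aligned with the rule chosen.

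The change is to wording only, but it amends the primary analysis of a protocol that already has ethics approval (Section 8.1). Holm costs power, as shown in the working: about 11 points in the worst case if unadjusted power is 70% (70 − 59), 9 if it is 80% (80 − 71) and 6 if it is 90% (90 − 84). A fixed order keeps full power for the first outcome but makes the second depend on it: if both tests have 80% power, the second is reached and significant in 64% (correlation 0) to 75% (0.9) of trials.

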Participants will be recruited from the general gynaecology clinics. Only patients who have already opted to undergo outpatient hysteroscopy will be invited to take part in the study and they will be made aware of the study at the time of the clinic appointment or shortly after. Interested parties will then be contacted by the research team to discuss the study in more detail at a time which is convenient for the patient. Written consent to enter the study will be sought from the participant in advance of their procedure and only after a full explanation has been given. The patient will be offered a study information leaflet. Whilst waiting for their hysteroscopy procedure, the patient will be offered a face-to-face appointment with a member of the research team to discuss the study and sign the written consent form if they wish to participate in the study. If it is more convenient for the patient, and to avoid unnecessary additional appointments for the patient, they may prefer to discuss the study and go through the consent by phone before confirming consent on the day of the procedure. Patients will have time to consider whether to take part in the study prior to their procedure day and will be informed that they can withdraw consent for participation in the study at any time. Participating or not participating in the study will have no effect on the timing of the outpatient hysteroscopy or the type of procedure performed. Patients will have the opportunity to choose which virtual reality scenario they wish to experience during the procedure (choice of 4 scenarios from beach, space, underwater and zen four seasons).

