At the time of their hysteroscopy. The patient will fill out the pre-procedure NRS score prior to entering the hysteroscopy room. The patient will then enter the outpatient hysteroscopy room where there will be the hysteroscopy team consisting of the lead hysteroscopist and the assistant, and also a single member of the research team who will have taken the study consent from the patient prior to their procedure. Following discussion with the hysteroscopist as usual, the patient will prepare for the procedure and position themselves on the procedure couch. Once comfortable, the member of the research team will help the patient to put on the VR headset (See appendix 1), and if the patient wishes, headphones. The virtual reality software will then start running and is controlled by the research team member, the software will run for the length of the procedure. The hysteroscopy team will be preparing the equipment as the virtual reality software is running. The member of the research team will remain in the room throughout the procedure to troubleshoot any issues with the headset or software and if necessary to stop the VR program. Following completion of the procedure the patient will fill out a NRS score prior to going home.

The VR software involves breathing exercises, relaxing music and a distracting immersive walk through a virtual environment. The scenario will be started and subsequently controlled by a member of the research team operating a tablet device. The hysteroscopy team will perform the procedure in exactly the same way as they would normally and any clinical decisions regarding potential procedures such as polypectomy, discontinuing or proceeding with the hysteroscopy will be made by the hysteroscopy team along with the patient in the usual way without any input from the research team member.

Maintaining appropriate clinical hygiene is of critical importance as the same headset will be used for different patients. The headset can be easily and effectively cleaned between use and the manufacturer (VR medical) provides a recommended cleaning regimen which we will use for the trial. After use, the VR device and controller should be cleaned with a damp microfibre cloth and disinfectant wipe, both the parts that have been in contact with the skin and the headbands.

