The timetable for the project is expected to run as follows. Three months for preparation and obtaining ethical approval. Recruitment is expected to start following this and we would expect to obtain the required number of participants by 3 months based on the average referral rate for outpatient hysteroscopy in the unit being 150 patients per month and a 20% study participation rate. Data analysis and preparing the final report would take a further 3 months.

Results will be recorded onto a pseudoanonymised database. Information will be collected from patients notes and imaging reports. Each patient will be allocated a study number and for each the following will be recorded:

- Age
- Parity
- Symptoms and duration
- Past medical history and co-morbidities
- BMI
- Previous surgery
- Current medication and medication used within the last 6 months
- Pain NRS (numeric rating score)
- Anxiety NRS

Length of hysteroscopy procedure  
Time in Outpatient Procedure room  
Procedure successfully completed (or not) and reason for failure if appropriate  
Complications  
Hysteroscopy findings  
Type of hysteroscopic procedure performed

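### Section 7 gives the pre-procedure NRS no role: a t test of post-procedure scores is valid but wastes baseline data that ANCOVA could use if scored before allocation is disclosed

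*Combined protocol and SAP*

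**What the plan says.** The Study Summary sets two primary outcomes: "Primary outcome measures are patient reported NRS (numeric rating score) for pain and anxiety". Section 3, repeated in Section 3.1, describes two completions: "The patient will be asked to fill out the NRS score prior to the hysteroscopy and following the hysteroscopy prior to leaving the clinic". Section 3 places the first of them: "The patient will fill out the pre-procedure NRS score prior to entering the hysteroscopy room". The second is before going home.

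Section 7 is the only analysis text, and its sentence on the primary outcome is "Means NRS scores will be compared between the 2 groups using the unpaired student's T test". No other section gives the pre-procedure score a use.

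Three points are left open:

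- **Time point compared.** The objectives in Section 2 are framed as whether "VR technology can reduce pain during outpatient hysteroscopy" (and likewise anxiety), and Section 6 ends the study at the last post-procedure questionnaire. Both point to post-procedure scores, but Section 7 does not say so.
- **Which scores are taken when.** That pain and anxiety are each scored at both times is a fair inference, not stated text. The data list in Section 3 has one entry beginning "Pain NRS (numeric rating score" and one for anxiety, neither with a time point.
- **When allocation is disclosed.** Section 3 says only that allocation is by computer and that "Neither the researchers nor the participants will be blinded as to which study arm they are in".

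**The concern.** A baseline measure of the outcome is collected and then not used. In a randomised comparison, ANCOVA of the post score on arm and pre score is, in large samples, at least as precise as a t test of either post scores or changes. With a minimum of 40 per arm, and no effect size, SD or power reported, that precision is worth having.

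A smaller harm follows from the unnamed endpoint. The wording permits a post-score or a change-score comparison, and in an unblinded trial that choice should not be open once data are seen. It is smaller because the post score is the default reading.

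The remedy has its own hazard. If participants know their arm when they complete the pre-score, that score may already carry an effect of allocation, and adjusting for it would bias the estimate. Section 3 makes early disclosure plausible: the trial is unblinded and "Patients will have the opportunity to choose which virtual reality scenario they wish to experience during the procedure".

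**Working it through.** **Inputs from the documents.** At least 40 per arm (Section 3); p < 0.05, taken as two-sided because sidedness is not stated (Section 7); 150 referrals per month × 20% participation = 30 recruits per month (Section 3).

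**The plan's own figure.** The 40 per arm cannot be reproduced, because its difference, SD and power are not given. Solved backwards, it corresponds to a true difference of 0.634 SD at 80% power (noncentral t; 0.626 SD by the normal approximation). I take d = 0.634 SD as the assumed effect; post-score power is then 79.96%.

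**Equal pre and post SDs (assumed), pre-post correlation r (assumed).**

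- Post score: effect d, 78 df. 95% CI half-width = 1.991 × √(2/40) = 0.445 SD.
- ANCOVA: effect d/√(1 − r²), 77 df. Half-width = 1.991 × √(2/40) × √(1 − r²).
- Change score: effect d/√(2(1 − r)), 78 df.
- Patients per arm for the post-score test to match ANCOVA's precision: 40/(1 − r²), rounded up.

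Example, r = 0.5: √(1 − 0.25) = 0.866; 0.634/0.866 = 0.732, giving 89.8% power; half-width 0.386 SD; 40/0.75 = 53.3, so 54 per arm, or 28 more patients, and 28/30 = 0.9 months.

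| r | ANCOVA power | Change-score power | ANCOVA half-width (SD) | Equivalent n per arm | Extra patients | Months |
|---|---|---|---|---|---|---|
| 0.1 | 80.3% | 55.1% | 0.443 | 41 | 2 | 0.1 |
| 0.3 | 83.5% | 65.8% | 0.425 | 44 | 8 | 0.3 |
| 0.5 | 89.8% | 80.0% | 0.386 | 54 | 28 | 0.9 |
| 0.6 | 93.8% | 87.9% | 0.356 | 63 | 46 | 1.5 |

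**Pain with a floor (assumed).** Simulated integer scores of 0–10, 60% of pre-scores zero, SDs 1.19 before and 2.42 after, shift 1.58 before bounding, 60,000 trials per setting. Power for post / change / ANCOVA:

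- observed r = 0.12: 78.6 / 73.8 / 78.7% (no gain)
- r = 0.25: 78.8 / 78.8 / 80.9%
- r = 0.41: 78.6 / 85.6 / 85.3%

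**Validity.** In simulated integer scores with no effect (4,000 runs per setting), type I error was 5.1–5.3% for the post-score t test and 4.8–5.3% for ANCOVA. Neither is at fault.

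**Choosing the better of post and change after seeing the data.** With no true effect and 200,000 trials per setting, two-sided type I error per outcome is 8.4–9.2% with equal SDs and 7.2–7.3% with floored pain. False positives favouring VR are 4.2–4.6% and 3.6–3.7%, against a nominal 2.5%.

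**Pre-score taken after disclosure.** Suppose knowing the allocation lowers VR-arm pre-scores by 0.2 SD (assumed). With equal SDs, ANCOVA shifts the estimate against VR by about r × 0.2: 0.02, 0.06, 0.10 and 0.12 SD at r = 0.1, 0.3, 0.5 and 0.6. Simulation agrees (0.019, 0.060, 0.103, 0.121). The post-score t test does not shift.

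**The case against.** The planned test is valid, and leaving a randomised comparison unadjusted is an efficiency choice, not a mistake. The gain has no anchor in the documents: on the assumptions above it runs from 0.4 percentage points of power at r = 0.1 to about 14 at r = 0.6, and for floored pain it is 0.1 points at r = 0.12. If post-procedure scores are the default reading, the selection harm is hypothetical, since no section mentions a change score. Most seriously, under early disclosure the assumed bias (0.02, 0.06, 0.10, 0.12 SD) exceeds the narrowing of the half-width (about 0.002, 0.02, 0.06, 0.09 SD) at every r shown. The recruitment equivalent is also modest: 30 per month for 3 months gives about 90 patients against the 80 needed.

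Most of this stands, and it limits the point without removing it. Validity is not in dispute. An unknown r does not argue against adjustment, because at r = 0.1 ANCOVA is no worse than the t test. The bias is the reason for making ANCOVA conditional on the order of steps, with the t test as fallback. Two details also stand but change nothing: the floored simulation used 0–10 where the protocol gives 0–11, and ANCOVA drops a patient with no pre-score.

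**Conclusion.** The point holds as a recommended change, with medium confidence. Section 7 assigns no role to a baseline that Section 3 collects, and it does not name the endpoint. The natural reading is a valid but less precise analysis.

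At a plausible r of 0.3 to 0.5 with equal SDs, adjustment is worth about 4 to 10 percentage points of power, or the equivalent of 8 to 28 patients. The benefit is likely for anxiety and uncertain for pain. All of these sizes depend on assumed r, SDs and effect. The advantage of ANCOVA depends on the pre-score preceding disclosure of allocation, on which the documents are silent. Naming the post-procedure score is needed whichever order applies.

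**What to change.** 1. **Section 7.** Replace the t test sentence with: *For each of pain and anxiety, the primary analysis compares the post-procedure NRS between arms by ANCOVA (linear regression) on arm and the matching pre-procedure NRS, reporting the adjusted mean difference with 95% CI. The unpaired t test of post-procedure scores is a sensitivity analysis.*
2. **Sections 3 and 3.1.** Name the post-procedure NRS as the primary endpoint.
3. **Section 3, data list.** Enter pre-procedure pain, post-procedure pain, pre-procedure anxiety and post-procedure anxiety as four items.
4. **Section 3.** State that the pre-procedure NRS is completed before the participant learns the allocation.
5. **Fallback.** If that order cannot be ensured, keep the unpaired t test as primary and insert *post-procedure* into the present sentence.

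The cost is wording, two more data items and one degree of freedom, with no extra patients. The order of steps on the day may need a small change. A patient without a pre-score is lost to the ANCOVA but stays in the sensitivity t test.
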